Statistical analysis plan

Title:

Does deciding not to participate in a lifestyle intervention affect the long-term change in psychosocial well-being for children with obesity?

Suggested authors:

[name]

[name]

[name]

[name]

[name]

[name]

Purpose:

In this plan for statistical analysis, we provide an overview of the study's context and objectives, as well as general aspects of data management and data analysis. The statistical analysis plan will be attached as a supplementary document upon submission.

Introduction

Childhood obesity is associated with an increased risk of developing non-communicable lifestyle diseases later in life(1-4), while reduced psychological well-being often occurs during childhood. Children living with obesity suffer from lower self-esteem, which have been associated with increased level of sadness and loneliness(5). They also experience higher degree of bullying/teasing(6, 7), have lower quality of life (8, 9) and increasing risk of depression (10) as compared to their peers living without obesity.

Family-centered lifestyle interventions including a multifactorial approach are still considered the first line of treatment when handling childhood obesity(11, 12). The literature suggest that this type of intervention can stabilize or to some extent reduce weight when treating children with obesity(12-14).

Previous studies have reported life stressors, societal norms of weight and body size, as well as earlier experiences with the health care system to be the primary determinants for caregivers not letting their children with obesity participate in lifestyle interventions(15-17).

However, no studies have been able to describe if deciding not to participate in a lifestyle intervention potentially affect the psychosocial well-being in children with obesity.

Objective

To investigate the impact in psychosocial well-being for children with obesity deciding not to participate in a family-centered lifestyle intervention (deciding not to participate group) compared to children who attended the intervention (intervention group), and to children never invited into the intervention (non-intervention group). As a secondary objective, we aim to investigate the effect that is not caused by the weight change by adjusting for this.

Material and methods

Design

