This is an observational cohort study investigating the impact in psychosocial well-being for children with obesity deciding not to participate in a lifestyle intervention. Data will be obtained from mandatory health check-ups at school, Danish national registries, and Danish National Well-being Questionnaire (DNWQ).

Participants

Children were screened by a community health nurse during school time. If the child's BMI (age- and sex-adjusted) was above 30 kg/m^2 , the parents would be informed and invited to participate in the local lifestyle intervention. If the parents accepted, they would be referred to the intervention. The intervention had a maximum duration of one year and typically consisted of 3-4 consultations with a specialized community health care nurse.

This study will include children with obesity with an inclusion visit between August 1st, 2014, and June 30th, 2020, from the city of Aarhus. February 1st, 2023, will be the last day of follow-up (figure 1). The inclusion visit will be defined as the day of deciding not to participate in the intervention (decided not to participate group), the first day of attending the intervention (intervention group), or the first observation with obesity (non-intervention group).

The groups

- Decided not to participate group: Children with obesity declining to participate in a lifestyle intervention.
- Intervention group: Children with obesity who attended the lifestyle intervention.
- Non-intervention group: Children with obesity never invited into the intervention.

Inclusion criteria

1. An inclusion visit between August 1st, 2014, and June 30th, 2020 (figure 1).
2. Obesity at time of referral as defined by the International Obesity Task Force (IOTF) guideline(18).
3. A measure of weight and height within 6 months before or after time of inclusion
4. Age at inclusion between 5 to 10 years of age.
5. A completed DNWQ at inclusion:
 - The deciding not to participate / non-intervention group - with a timeframe between 6 months prior to and 6 months after inclusion.
 - The intervention group - with a timeframe between 10 months prior to and 2 months after inclusion.
6. A completed DNWQ at follow-up (1 to 3 years after inclusion).

Exclusion criteria

1. Children first decided not to participate, but subsequently accepting the intervention.

Outcome

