The outcome of this study will be the dichotomized responses at follow-up to specific items obtained from the DNWQ. The DNWQ is used to examine how primary school children perceive their psychosocial well-being and learning environment in school. The DNWQ has been a mandatory assignment for the public schools in Denmark and was introduced in 2015. DNWQ consist of 20 items for children in 0th to 3rd grade assessed using a three-point Likert scale ranging from 1 to 3. For children in 4th to 9th grade the DNWQ consist of 40 items assessed on a five-point Likert scale ranging from 1 to 5.

For this study we have selected 7 items to best describe the psychosocial well-being in our cohort. We will include completed questionnaires at time of inclusion and at follow-up. At follow-up, we will prioritize completed questionnaires closest to two years from time of inclusion visit.

All answers will be dichotomized into: Good well-being / Poor well-being, depending on the item. Responses 1 and 2 for grades 0-3 and response 1-3 for grades 4-9 will be characterized as poor well-being.

The psychosocial well-being items:

Question 1:

Are you happy with your school? (0th to 9th grade)

Question 2:

Do you feel lonely at school? (0th to 3rd grade)

Do you feel lonely? (4th to 9th grade)

Question 3:

Is anyone teasing you so that you feel sad? (0th to 3rd grade)

Have you been bullied this school year? (4th to 9th grade)

Question 4:

Does your stomach ache when you are at school? (0th to 3rd grade)

How often does your stomach ache? (4th to 9th grade)

Question 5:

Are you good at solving your problems? (0th to 3rd grade)

How often can you find a solution to problems, just by trying hard enough? (4th to 9th grade)

Question 6:

Can you concentrate during class? (0th to 9th grade)

Question 7:

Are you good at helping each other in class? (0th to 3rd grade)

Most students in my class are friendly and helpful. (4th to 9th grade)

Data sources and study variables

Data sources

TM-Sund: TM-Sund is a data capturing tool used by community health nurses and has been used to record data on height and weight obtained from health check-ups at the school and data on children attending or deciding not to participate in the intervention.

The National Registers at Statistic Denmark (DST): DST will be used to identify relevant co-variables such as proxies for Socioeconomic status, immigration background, family structure and psychiatric diagnoses of the child or parents.

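### The rules on later acceptance and on never being invited have no end date, so an event after the outcome questionnaire can decide who is analysed in Tables 3 and 4

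*Combined protocol and SAP*

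**What the plan says.** Under Participants, time zero for decliners is fixed by their decision: "The inclusion visit will be defined as the day of deciding not to participate in the intervention". For the other two groups it is "the first day of attending the intervention (intervention group), or the first observation with obesity (non-intervention group").

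Membership then depends on later events. The only exclusion criterion is "Children first decided not to participate, but subsequently accepting the intervention". The third group is defined under The groups as "Non-intervention group: Children with obesity never invited into the intervention". Neither sentence says up to when the later event counts.

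The inclusion criteria require "A completed DNWQ at follow-up (1 to 3 years after inclusion"), and the Outcome section prefers the questionnaire nearest to two years. The one outer date is a calendar date common to all children: "February 1st, 2023, will be the last day of follow-up". It is not linked to the exclusion rule or to the definition of the non-intervention group.

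Statistical methods and Tables 1 to 4 plan McNemar tests, crude and multivariable logistic regression, an exploratory model adjusted for change in BMI z-score, and stratified analyses. None keeps the excluded later accepters, and no table reports how many there were.

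**The concern.** Group membership should be settled by what is known at inclusion, or at the latest by the time the outcome is measured. As written, a child who declined, completed the follow-up DNWQ and accepted a year after that is removed, although the exposure during the outcome period was the one under study. A non-intervention child first invited after the outcome DNWQ likewise leaves that group.

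If later acceptance or invitation is related to follow-up well-being, the remaining children are selected on the outcome. Table 3 is affected through the decliners. Table 4 is affected through both groups, where the effects may cancel. The planned adjustment for well-being at inclusion removes only the part of the selection that runs through baseline.

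There is also a question of meaning. The title asks "Does deciding not to participate in a lifestyle intervention affect the long-term change in psychosocial well-being for children with obesity". After the exclusion, the group consists of children whose families declined and never changed their minds, which is a narrower group than those who declined.

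**Working it through.** The documents give no sample size, number of later accepters, timing of acceptance or prevalence of poor well-being. There is therefore no plan figure to reproduce. Steps 2 to 4 use assumed inputs.

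**1. Time after the outcome in which an event can still count.** Suppose records are searched to 1 February 2023, which the plan does not say.
- Last inclusions, 30 June 2020: 2.59 years to the end. With the DNWQ at 2 years, 2.59 − 2 = 0.59 years lie after the outcome.
- Earliest eligible decliners or non-intervention children: these need a DNWQ within 6 months of inclusion, and the Outcome section says "The DNWQ has been a mandatory assignment for the public schools in Denmark and was introduced in 2015". A first DNWQ in January 2015 allows inclusion on 1 August 2014, which is 8.50 years to the end and 8.50 − 2 = 6.50 after the outcome. A first DNWQ on 31 December 2015 allows inclusion from 30 June 2015, giving 7.59 and 5.59 years.

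Ending the decliner rule at the child's own follow-up DNWQ reduces the time after the outcome to zero for that rule.

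**2. Effect of selection on the OR.** Let *r* be the prevalence of poor follow-up well-being, *s* the share of decliners removed, and *k* the ratio of removal probabilities, poor to good. Then a0 = s/(rk + 1 − r), a1 = k·a0, and with a true OR of 1 the observed OR is (1 − a1)/(1 − a0). Example with r = 0.30, s = 0.05, k = 2: a0 = 0.05/1.30 = 0.0385, a1 = 0.0769, OR = 0.9231/0.9615 = 0.96.

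| Removed (r = 0.30) | k = 2 | k = 0.5 |
|---|---|---|
| 5% | 0.96 | 1.03 |
| 15% | 0.87 | 1.11 |
| 30% | 0.70 | 1.27 |

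Milder dependence gives less: 0.99 (k = 1.25, 5% removed), 0.97 (k = 1.25, 10%) and 0.95 (k = 1.5, 10%). With k = 1 the OR is 1.00. It is also 1.00 after adjustment if removal depends only on well-being at inclusion, and in Table 4 if both groups are selected equally.

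**3. What the cut-off gains.** Take 15% removed, 5% before and 10% after the outcome DNWQ. Apply the formula in two stages, with the second share 0.10/0.95 = 0.105 and *r* updated after the first.
- k = 2 throughout: 0.960 × 0.911 = 0.875 under the present rule, 0.960 with the cut-off.
- k = 0.5 throughout: 1.031 × 1.071 = 1.104 under the present rule, 1.031 with the cut-off.
- Only the later removals depend on follow-up well-being: 0.912 (k = 2) or 1.071 (k = 0.5) becomes 1.000.

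**4. Dilution when later accepters are put back.** Take an intervention-group risk of 0.30 and a true OR of 1.5, so the decliners' risk is 0.391. If a share *s* of the decliners instead has risk 0.30, the OR is 1.47, 1.42 or 1.34 for *s* = 5%, 15% or 30%.

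**The case against.** The documents show no route from the outcome to removal. Invitation follows a nurse's BMI screening. DNWQ answers come from a ministry source separate from the nurses' records, and nothing says the nurses see them. The Introduction attributes non-participation to life stressors, weight norms and earlier health-care experience. This stands as a reason not to presume strong selection. It does not exclude an indirect link, since whatever lies behind poor well-being could also prompt acceptance.

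The exclusion is openly declared, and it avoids counting as decliners children who also attended. This stands for acceptances before the outcome DNWQ. It gives no reason to remove a child for one that came after.

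A reader might infer three stronger things that the documents do not support.
- *That the results will be materially biased.* The ORs of 0.70 and 1.27 need 30% of decliners removed, with every removal dependent on follow-up well-being. No count or association in the documents points there.
- *That early inclusions are screened for up to 8.5 years and so selected far more strictly than late ones.* This needs a search to February 2023, and acceptance still possible for children then roughly 12.6 (5 + 7.6) to 18.5 (10 + 8.5) years old. Neither is stated. If 5% accept within 2 years at a constant rate, h = −ln(0.95)/2 = 0.0256 per year, and 1 − exp(−ht) gives 6.4% removed among the last inclusions and 17.7 to 19.6% among the earliest. If acceptance is early (median 6 months), the figures are 5.2% and 5.3%, no material difference.
- *That children should be reassigned by their earliest qualifying visit.* This could move an unknown number out of the intervention and decliner groups and change both tables. The data source is also not said to record invitations, so many may be undatable.

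**Conclusion.** The point holds in a limited form and is worth fixing. Following the rules as written lets events after the outcome determine group membership, and no planned analysis or count would reveal how much this matters. This rests on the text alone.

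That the odds ratios are biased does not follow from the text. It requires removal to be related to follow-up well-being beyond the baseline covariates. Direction and size cannot be determined from the documents, and at 5% removed the illustrated effect is negligible even with removal doubled or halved.

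Excluding children who accept before the outcome DNWQ is a legitimate choice, provided the contrast is described as sustained non-participation up to that questionnaire.

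**What to change.** 1. Exclude a decliner only if acceptance came before that child's own follow-up DNWQ, using first attendance if no acceptance date is held. A child who accepts after it stays in the decliner group and is counted only there.
2. Add to Tables 3 and 4 a sensitivity analysis that returns the excluded later accepters who have a follow-up DNWQ to the decliner group, from the day of declining, and does not count them in the intervention group.
3. Report how many decliners later accepted, split into before and after their follow-up DNWQ.
4. State that the main contrast is sustained non-participation up to the follow-up DNWQ.
5. State the date up to which never being invited is assessed. Only if invitations can be dated, report how many children were first invited after what would have been their follow-up DNWQ. Do not reallocate children between groups in the main analysis.

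The cost is some SAP wording, a comparison of two dates per decliner, and one extra run per table. The decliner part needs no new source: the plan already uses the dates of declining and of first attendance as inclusion visits, and TM-Sund holds data on both events. The downside is some dilution in the sensitivity analysis. Selection before the follow-up DNWQ remains in the main analysis, and confounding by the decision to decline remains in both.

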The Department of IT and Learning (STIL): The DNWQ will be obtained from STIL, Ministry of Children and Youth.

Study variables:

We wish to include the following co-variates at inclusion:

- BMI z-score (e.g. 3.0 SD) (19)
- Sex (girl/boy)
- Highest completed Household Education (HHE)
 - “Short”: Primary school (UNESCO’s International Standard Classification of Education (ISCED) level 1-2).
 - “Middle”: Highschool, vocational education, and similar shorter education (ISCED level 3-5).
 - “Long”: Tertiary education at bachelor level or higher (ISCED level 6-8)
- Immigration status (Danish origin / immigrants 1. or 2. generation)
- Disposition for mental illness (lifetime) (yes / no)
- Mental illness, child (lifetime) (yes / no)
- Family structure (two caretakers / not-two caretakers)

Statistical methods:

All statistical analyses will be performed using Stata/SE 15 (StataCorp LP, College Station, Texas, USA). All statistical tests will be two-sided with a significance level at 0.05.

For the characteristics at inclusion

- Normally distributed data will be analyzed using a one-way ANOVA (several means) and a t-test (two means).
- Non-normally distributed data will be analyzed using a Wilcoxon ranksum test (2 groups) and Kruskal-Wallis test (> 2 groups).
- Categorical variables will be analyzed using a Fisher's exact test.

For missing data (education, immigration status, and family-type), a multiple imputation (MI) with chained equations will be utilized to replace missing values with imputed values. Rubin's rule will be applied to obtain overall estimates of 100 imputed datasets.

We will perform the analyses in several steps:

Firstly, the McNemar's test will be used to investigate potential change in psychosocial well-being from time of inclusion to follow-up for each of the dichotomized items (Q1-Q7) in all three groups. All items will be dichotomized into: Good well-being/Poor well-being.

Secondly, the impact in psychosocial well-being for children declining participation will be compared to the intervention group and to the non-intervention group by a logistic regression. The logistic regression analysis will be reported as both a crude (only including the outcome and the groups) and a multivariable model. The psychosocial well-being at inclusion will act as an explanatory variable in the models.

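### The within-group McNemar tests pool children who switch from the 3-point to the 5-point questionnaire with children who do not, so an apparent change in well-being may be a change of form

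*Combined protocol and SAP*

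**What the plan says.** The Outcome section describes two questionnaires: "DNWQ consist of 20 items for children in 0th to 3rd grade assessed using a three-point Likert scale ranging from 1 to 3", and "For children in 4th to 9th grade the DNWQ consist of 40 items assessed on a five-point Likert scale ranging from 1 to 5". One rule makes both binary: "Responses 1 and 2 for grades 0-3 and response 1-3 for grades 4-9 will be characterized as poor well-being".

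Q1 and Q6 keep one wording across all grades. Q2, Q3, Q4, Q5 and Q7 each have two wordings. Q3, for example, asks the younger children "Is anyone teasing you so that you feel sad? (0th to 3rd grade") and the older children "Have you been bullied this school year? (4th to 9th grade").

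The inclusion criteria set "Age at inclusion between 5 to 10 years of age" and "A completed DNWQ at follow-up (1 to 3 years after inclusion"), with preference for the questionnaire nearest two years.

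As the first analysis step, "the McNemar's test will be used to investigate potential change in psychosocial well-being from time of inclusion to follow-up", item by item in each group. That makes 7 × 3 = 21 tests at two-sided 0.05. Logistic regression then compares the groups, with well-being at inclusion as an explanatory variable and up to seven prioritized co-variates. Questionnaire form, grade and age are not among those co-variates, are not in the exploratory model for BMI z-score change, and are not among the planned strata. Table 1 shows age by group. Table 2 prints both wordings but gives one row per answer category for the two forms together.

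**The concern.** McNemar compares the number of children who go from good to poor with the number who go from poor to good. It reads the imbalance as change, which requires both answers to come from the same measure. The ages and follow-up times in this design ensure that some children cross from grade 3 to grade 4 in between. Their second answer is on a different scale and, for five items, to a different question. Being teased to the point of sadness is not the same thing as having been bullied during the school year.

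The common cut removes the problem only if both forms yield the same share of poor answers in the same children. The plan offers no evidence of that. The coding assigns 2 of 3 categories (67%) and 3 of 5 categories (60%) to poor, but category counts do not tell us how children answer.

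What is at stake is the conclusion of the first step. A significant improvement or decline within a group could come from the form alone, and a within-group test has no comparator to reveal it.

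**Working it through.** The plan gives no sample size, age distribution, item prevalence or form mix, so there is no figure of its own to reproduce. The inputs below are assumptions unless marked as from the plan.

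**1. Share who switch form.** Take inclusion age as uniform from 5 to U (U = 10, or just under 11; age limits from the plan), start of 4th grade at age T (assumed 9.5 to 11), and follow-up f years (1-3, target 2; from the plan). With the baseline questionnaire on the inclusion day, the share is

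[min(T, U) − max(T − f, 5)] / (U − 5).

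- U = 10, T = 9.5, f = 2: (9.5 − 7.5)/5 = 40%.
- U = 10, T = 10.5, f = 2: (10 − 8.5)/5 = 30%.
- U = 10, T = 11, f = 2: (10 − 9)/5 = 20%.

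Spreading the baseline questionnaire over the plan's windows (−6 to +6 months, or −10 to +2 months for the intervention group) raises the top value to 45.6%. The range is therefore about 20-46% at two years, 0-26% at one year and 40-66% at three years.

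**2. McNemar with no true change.** Assume 40% poor on the younger form, p% poor on the older form, a latent correlation of 0.4 between the two occasions, and 5% of children on the older form both times. For p = 25 the bivariate normal gives these probabilities:

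- switchers: poor-to-good 0.248, good-to-poor 0.098;
- younger form twice: 0.178 each way;
- older form twice: 0.143 each way.

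At 40% switching, the pooled probabilities are

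- poor-to-good: 0.40 × 0.248 + 0.55 × 0.178 + 0.05 × 0.143 = 0.204;
- good-to-poor: 0.40 × 0.098 + 0.55 × 0.178 + 0.05 × 0.143 = 0.144.

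The false net change is 0.204 − 0.144 = 0.06, which is 0.40 × (0.40 − 0.25). The number of discordant pairs is binomial with probability 0.204 + 0.144. Given that number, the exact test compares the split with one half. Rejection rates (%) at n = 200 pairs:

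| Older form, % poor | 20% switch | 30% | 40% | 45% |
|---|---|---|---|---|
| 25 | 9 | 16 | 26 | 32 |
| 30 | 6 | 9 | 13 | 16 |
| 35 | 4 | 5 | 6 | 7 |
| 40 (forms agree) | 4 | 4 | 4 | 4 |

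- If the older form gives more poor answers (50-55%), the rate is 9-25% at 30-40% switching.
- For 25-30% poor and 30-40% switching, it is 5.5-13% at n = 100 and 15-50% at n = 400.
- Same-form pairs alone give 3-4%. The exact test is slightly conservative; the asymptotic version gives about 5%.

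A different model points the same way. With 15% discordance in each direction, an uncorrected McNemar test, n = 200 and 40% switching, form shifts of 6.7, 10 and 20 points give 10.8%, 17.9% and 54.6%.

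**3. Group odds ratios with a true value of 1.** If both groups have the same form mix at follow-up, both have the same share poor and the odds ratio is 1.00. Now suppose 40% of one group and 60% of the other are on the older form, with p = 25:

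- 0.40 × 0.25 + 0.60 × 0.40 = 0.34;
- 0.60 × 0.25 + 0.40 × 0.40 = 0.31;
- odds ratio (0.34/0.66)/(0.31/0.69) = 1.15, or 1.14 with the baseline answer in the model.

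At 45% versus 55% the baseline-adjusted value is 1.07. Both shrink as the forms come closer (1.04 and 1.02 at p = 35), and the direction reverses if the other group is the older one.

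**The case against.** The strongest reply is that McNemar is a preliminary step. The objective is a comparison between groups, Tables 3 and 4 report only between-group odds ratios, and a form effect common to all groups leaves a null odds ratio at 1.00. That stands, and it limits the weight of the point.

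A reader might go further and infer that the odds ratios are themselves biased. The documents do not support this. Inclusion is a different event in each group (declining, first attendance, first observed obesity), so a different age or form mix is possible, but nothing gives its size or direction. Under the uniform-age model, a 40% versus 60% gap needs about one year's difference in mean age, which Table 1 would show. Nor do the unequal baseline windows establish it: alone they move the adjusted odds ratio by at most about 1%.

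A reader might also infer that the plan overlooked the two forms. It did not. It matches items across forms, sets a cut for each form with the middle category counted as poor, and prints both wordings in Table 2. What it lacks is evidence that the forms agree, or an analysis that does not need them to.

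Finally, the size depends on the inputs. With a 5-point difference between forms and up to 40% switching, rejection at n = 200 is 4-6%, essentially nominal.

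**Conclusion.** The point holds for the within-group step. For children who change form, McNemar as planned cannot tell a change in well-being from a change of questionnaire, and the pooled result inherits this. That follows from the plan's text and needs no assumption.

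The size does rest on assumptions: age distribution, age at 4th grade, item prevalence, correlation and n. At n = 200, with 40% poor on the younger form and no true change, false rejection is about 6-9% at 20% switching and 9-26% at 30-40% switching if the older form gives 25-30% poor. It is about 4-6% if the older form gives 35%, and about 4% if the forms agree.

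For the between-group odds ratios the concern is conditional on a difference in form mix that the documents neither show nor exclude. It should be checked and does not justify restructuring the main models. The correction is worth making because it changes what the first step can conclude and uses data already held.

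**What to change.** 1. Report McNemar separately for same-form pairs and for switchers. Base any statement about change in well-being on the same-form pairs. Give the switcher and pooled results only with the caveat that they may reflect the change of form.
2. Tabulate form pattern (younger/younger, younger/older, older/older) by group, for example in Table 1.
3. Add a sensitivity version of the multivariable model with form at follow-up as a co-variate. Leave the crude model and the prioritized co-variate list unchanged. Under the cap of one co-variate per ten less-common outcomes, putting form first on that list would displace a pre-specified co-variate at every count from 10 to 79, to address a bias of unknown size.

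A logistic analysis restricted to same-form children is not advised unless each group has enough older/older children to estimate a form term. For ages 5-10, that share is 0% if 4th grade starts at 10.5, and 0.3-2.5% if it starts at 10.

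Cost: SAP wording, one table row and one extra model. The 21 McNemar tests become 42, or 63 if pooled results are kept. Each test has fewer pairs: at 20-46% switching, about 109-160 of 200 remain on the same form. Those pairs are mostly younger children (63-100% younger/younger under the assumed ages), so the result does not describe the whole cohort, and the report should say so.

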Poor well-being (yes)						
Question 4: Does your stomach ache when you are at school? (0-3 grade) How often does your stomach ache? (4-9 grade)						
Good well-being (no/rarely)						
Poor well-being (yes/often)						
Question 5: Are you good at solving your problems? (0-3 grade) How often can you find a solution to problems, just by trying hard enough? (4-9 grade)						
Good well-being (yes/often)						
Poor well-being (no/rarely)						
Question 6: Can you concentrate during class?						
Good well-being (yes)						
Poor well-being (no)						
Question 7: Are you good at helping each other in class? (0-3 grade) Most students in my class are friendly and helpful? (4-9 grade)						
Good well-being (yes)						
Poor well-being (no)						

Table 3:

Logistic regression analyses comparing the decided not to participate group and the intervention group.

The multivariable model will be adjusted for up to 1 co-variable per 10 observations.

Decided not to participate group vs. intervention group	OR (95% CI), p-value
Q1 – Enjoyment at school	
Univariable logistic regression	
Multivariable logistic regression	
Q2 – Feelings of loneliness at school	
Univariable logistic regression	
Multivariable logistic regression	
Q3 – Experiences of bullying	
Univariable logistic regression	
Multivariable logistic regression	
Q4 – Experiences of stomach aches	
Univariable logistic regression	
Multivariable logistic regression	
Q5 – Problem-solving	
Univariable logistic regression	
Multivariable logistic regression	
Q6 – Concentration in the classroom	
Univariable logistic regression	
Multivariable logistic regression	
Q7 – Helpfulness in the classroom	
Univariable logistic regression	
Multivariable logistic regression	

Table 4:

Logistic regression analyses comparing the decided not to participate group and the non-intervention group.

The multivariable model will be adjusted for up to 1 co-variable per 10 observations.

Decided not to participate group vs. non-intervention group	
	OR (95% CI), p-value
Q1 – Enjoyment at school	
Univariable logistic regression	
Multivariable logistic regression	
Q2 – Feelings of loneliness at school	
Univariable logistic regression	
Multivariable logistic regression	
Q3 – Experiences of bullying	
Univariable logistic regression	
Multivariable logistic regression	
Q4 – Experiences of stomach aches	
Univariable logistic regression	
Multivariable logistic regression	
Q5 – Problem-solving	
Univariable logistic regression	

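### The logistic models for Tables 3 and 4 take no account of shared schools, classes and households, so their confidence intervals may be too narrow by an amount the documents cannot determine

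*Combined protocol and SAP*

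**What the plan says.** Statistical methods says that the group that declined will be "compared to the intervention group and to the non-intervention group by a logistic regression", in a crude and a multivariable form, with well-being at inclusion as an explanatory variable. Tables 3 and 4 report "OR (95% CI), p-value" for each of seven items, and "All statistical tests will be two-sided with a significance level at 0.05". The plan names no robust variance, random effect or GEE, and no school, class or household identifier. None of the seven listed covariates is a school, class or household.

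Participants describes how the cohort arose. "Children were screened by a community health nurse during school time", and the cohort is drawn "from the city of Aarhus" over about six years. Parents of a child above the BMI threshold were invited and could accept or decline. The non-intervention group was never invited, and no reason is given. The only exclusion criterion concerns children who first declined and later accepted, so siblings can both enter.

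Outcome says the questionnaire examines "how primary school children perceive their psychosocial well-being and learning environment in school". Question 7 asks about the class in both grade versions; in the upper grades the statement is "Most students in my class are friendly and helpful". Question 1 asks about the school. Questions 2 to 6 ask about the child.

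**The concern.** Ordinary logistic standard errors assume that, given the covariates, one child's answer carries no information about another's. Two study children in the same class who answer Question 7 are rating the same object, and two in the same school who answer Question 1 are judging the same school. Siblings share a home and, because parents decide on participation, will tend to share a group as well.

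Positive correlation in the outcome inflates the error of a group contrast only to the extent that group membership clusters in the same units. Where both cluster, the ordinary standard errors are too small, the intervals in Tables 3 and 4 are too narrow, and a difference between groups can be called significant too often.

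**Working it through.** The plan gives no sample size, number of schools, children per school or ICC, so there is no figure of its own to reproduce. What follows is a sensitivity range.

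**Inputs.** From the documents: two-sided alpha of 0.05 (critical value 1.96). Assumed: m = 3 to 10 study children per school, outcome ICC 0.02 to 0.10, and an ICC for group membership of 0 (varies freely within school), 0.3 (partly clustered) or 1 (constant within school).

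**Formulas.**
- Design effect: DEFF = 1 + (m − 1) × ICC(outcome) × ICC(group)
- True type I error: 2 × [1 − Φ(1.96 / √DEFF)]

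**Results by school.**

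| ICC(group) | m | ICC(outcome) | DEFF | Type I error |
|---|---|---|---|---|
| 0 | any | any | 1.00 | 5.0% |
| 0.3 | 3 | 0.02 | 1 + 2 × 0.02 × 0.3 = 1.01 | 5.1% |
| 0.3 | 10 | 0.05 | 1 + 9 × 0.05 × 0.3 = 1.14 | 6.6% |
| 0.3 | 10 | 0.10 | 1 + 9 × 0.10 × 0.3 = 1.27 | 8.2% |
| 1 | 3 | 0.02 | 1 + 2 × 0.02 = 1.04 | 5.5% |
| 1 | 10 | 0.05 | 1 + 9 × 0.05 = 1.45 | 10.4% |
| 1 | 10 | 0.10 | 1 + 9 × 0.10 = 1.90 | 15.5% |

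In the last row the ordinary standard error is too small by a factor of √1.90 = 1.38.

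**Results by class or household.** With about two study children per unit and an outcome ICC of 0.10, DEFF is 1 + 1 × 0.10 × 0.3 = 1.03 (5.3%) with partial clustering of group, and 1.10 (6.2%) if the two always share a group.

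**Simulation under no group effect.** 40 schools of 8 children, outcome prevalence about 30%, 1,000 runs per setting, ICCs set on the logit scale. Rejection rates at nominal 5%:

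| ICC(outcome) | ICC(group) | Ordinary SE | Cluster-robust SE |
|---|---|---|---|
| 0.05 | 0 | 5.1% | 5.5% |
| 0.05 | 0.3 | 5.6% | 5.8% |
| 0.10 | 0.3 | 6.1% | 5.0% |
| 0.05 | 1 | 8.4% | 5.3% |
| 0.10 | 1 | 10.2% | 6.0% |

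The Monte Carlo standard error near 5% is √(0.05 × 0.95 / 1000) = 0.7 percentage points, so the first two rows show no real difference between the methods. The last two rows confirm the direction of the formula. They fall somewhat below it (for m = 8 and outcome ICC 0.10 it gives DEFF 1.70 and 13.3%), as expected because an ICC set on the logit scale is smaller on the yes/no scale.

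**The case against.** The strongest reply is that Participants makes acceptance a decision of the parents. For Table 3, declining or attending can therefore differ between children in one school, and the case nearest to that has almost no inflation. This largely stands. It does not remove sibling correlation, since one parental decision style may cover both children, but that effect is small. Nor does it cover Table 4, because the plan does not say why some children were never invited.

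The cluster unit also matters. Inclusion runs over about six years, ages 5 to 10, with follow-up one to three years later, so children from one school may be rating different classes in different years. That weakens the case for large clusters on Question 7. Adjustment for well-being at inclusion, and for household education and immigration status where the covariate limit allows them, may absorb part of any stable school or family difference; the relevant ICC is the one that remains.

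A reader might infer that the planned intervals and p-values are simply invalid, or that 15.5% is the expected error rate. The documents support neither. Every cluster size and ICC is assumed, and the upper figure needs group membership to be constant within school, which conflicts with family-level choice in Table 3. A reader might also infer that nurses invited by school. Participants describes invitation by a BMI threshold, and school- or nurse-driven non-invitation is only a possibility.

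**Conclusion.** The omission is real: the plan assumes independent children in a cohort where shared schools are very likely and shared classes and households are possible, and it does not discuss this. The consequence is that intervals may be too narrow, not that they are shown to be wrong. Under the stated assumptions true type I error runs from about 5% to about 8% with no or partial clustering of group membership, and reaches 15.5% only in the extreme case. The concern is greatest for Questions 7 and 1 and for the comparison with never-invited children, if non-invitation followed school or nurse. It is probably small for decliners against attenders. A change is worth making because it is cheap, needs no ICC, and cost little in the simulation when clustering was harmless.

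**What to change.** Fit the logistic models for Tables 3 and 4 with cluster-robust standard errors by school, provided a school identifier is available and there are enough schools. State in advance whether school at inclusion or at follow-up defines the cluster, since the outcome is read at follow-up and children may have moved. Report the number of schools and of sibling sets. If no school key is delivered, cluster by household and say that this handles only sibling correlation, not correlation within school or class.

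The cost is one variance option in the model command plus a school or household key, which the plan does not currently list among its variables. Point estimates are unchanged. Intervals will usually be slightly wider, though this is not guaranteed. Robust errors are unreliable with few clusters, so the number of schools should be known before they are made the main analysis.
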